| | From an immunological point of view, the importance of the PD-1/PD-L1 axis has been shown in tumour mechanisms of resistance to the immune system, in particular by inhibiting lymphocyte action. Combining RF with targeted anti-PD-1/PDL-1 therapies could therefore be an interesting therapeutic option to control metastases distant from those treated with RF. |
| OBJECTIVES | Primary objective: To evaluate the RF-induced immune response to lung metastases of colorectal cancers (CRC). The radiofrequency-induced immune response will be jointly evaluated in 3 ways: by measuring changes to lymphocyte infiltration of metastasis tumour stroma, by quantifying the PD-1 and PD-L1 interaction by immune Förster Resonance Energy Transfer (iFRET), and by assaying blood lymphocyte sub-populations. Secondary objectives: — To evaluate the impact of RF on tumour activity by measuring the level of circulating tumour cells and circulating DNA, along |
| | with as the expression of the PDL-1 ligand on tumour cells. - Clinical evaluation with monitoring of metastatic disease and especially RF-treated sites - Evaluation of procedure-related complications (RF and biopsies) |

| | Primary endpoint: |
|--------------------|---|
| | Lymphocyte infiltration rate on histological analysis of metastases. Biopsy samples will be taken before RF and 4-6 weeks after the first RF in a second procedure on another initially untreated metastasis. A lymphocyte infiltration rate of 20% or more is considered significant. A comparative measurement of lymphocyte infiltration rates will be performed. |
| ENDPOINTS | A blood assay of NK, CD4, CD8 T cells and their HLADR+ activated sub-population, CD25+, CD38+, will be performed before, then 30 minutes after each RF, in order to evaluate distribution changes. |
| | Secondary endpoints: |
| | Rate of circulating tumour cells and of circulating DNA before and after each RF (before RF, at 30 minutes and on D1 after RF). Quantification of PDL-1 ligand expression on tumour cells before and after RF from histological samples Assessment of the progress of treated sites and of any distant metastatic disease by scans at 3, 6, 9 and 12 months, as part of standard follow-up. Complications will be graded (1 to 5) according to version 5 of the NCI-CTAE scale. |
| STUDY DESIGN | Prospective single-centre pathophysiology study |
| | Patient aged 18 years or over. WHO performance status ≤ 2. Histologically confirmed colorectal cancer. Resected primary tumour. Lung metastases bilateral (or unilateral if: number ≥ 5 and requiring two interventions), maximum diameter ≤ 4 cm, stable or slowly progressive (radiologically defined), with or without chemotherapy, eligible for radiofrequency therapy. Thorax-abdomen-pelvis CT scan and/or PET scan: performed within 8 weeks prior to inclusion, finding lung metastases of which no more than 10 can be |
| | treated with radiofrequency during both times (supplemental metastases being considered untreatable with radiofrequency due to their small size). |
| | Inclusion criterion No. 7 was deleted during MS2. Decision on local treatment taken during the multidisciplinary meeting or during an Interventional Radiology opinion meeting (no contraindication). Life expectancy ≥ 3 months. Free, informed and written consent signed by the participant and the investigator (on the day of inclusion at the latest and |
| INCLUSION CRITERIA | before any tests required by the study). 11. Patient with social security cover in accordance with Article 1121-11 of the French public health code. |

| EXCLUSION CRITERIA | Non-lung or liver metastases. Contraindication to general anaesthesia. Contraindication to radiofrequency treatment tumour localization (< 1 cm of the hilus), respiratory failure (FEV1 < 1 l), Pregnant or breastfeeding woman. Concomitant inclusion in another interventional radiology study. Patient incapable of following and adhering to research procedures for geographical, social or psychological reasons. Patient deprived of freedom or subject to a legal protective measure. Previous treatment with hormone therapy. |
|---|--|
| STUDY TREATMENTS/STRATEGIES/PROCEDU RES | Lung radiofrequency treatment of lung metastases of colorectal cancer. The procedure is performed under general anaesthesia. A RF needle is deployed, under strict asepsis, into the metastasis under imaging guidance. Once deployed, heating is performed to destroy the lesion. Each patient will undergo 2 procedures, to treat all metastases Biopsy samples are taken from a location before the heating phase. |
| STUDY SIZE | 20 patients |
| STUDY DURATION | Duration of the inclusion period: 24 months Duration of participation of each patient: 12 months Total study duration: 36 months |
| DATA STATISTICAL ANALYSIS | Number of subjects required This exploratory study is not based on a statistical hypothesis but on feasibility criteria in terms of recruitment. 20 patients will be included in this study Statistical analyses Patient characteristics will be described for the eligible and eligible evaluable populations: • Compliance with eligibility criteria, • Socio-demographic characteristics, • Clinical and tumour characteristics, • Performing procedures (RF, radiological examinations). Analysis of primary and secondary endpoints: • will concern the eligible and evaluable population. • Quantitative variables will be described from mean values (+/-sd) if the normality hypothesis is met, and otherwise from nonparametric statistics (median, range, quartiles). • Qualitative variables will be described based on frequency, percentage and 95% confidence interval (binomial law). |
| EXPECTED BENEFITS | Better understanding of radiofrequency-induced pathophysiological and immunological mechanisms of lung metastases with the possibility of developing combined RF/immunotherapy treatments an evaluation of metastatic disease activity with a new endpoint consisting of the circulating tumour cell (CTC) level |

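### Complications are assigned to the eligible and evaluable population with no all-treated set named, so some treated patients could drop out of the complication rate (minor)

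*Combined protocol and SAP*

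**What the plan says.** The secondary objectives in the synopsis include "Evaluation of procedure-related complications (RF and biopsies"), and the secondary endpoints include the matching measure: "Complications will be graded (1 to 5) according to version 5 of the NCI-CTAE scale".

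Under DATA STATISTICAL ANALYSIS, the analysis of primary and secondary endpoints "will concern the eligible and evaluable population". The same section names two sets for the baseline description: "Patient characteristics will be described for the eligible and eligible evaluable populations". The evaluable set can therefore be smaller than the eligible one, and the endpoints are placed in the narrower set. Qualitative variables are to be given as a frequency, a percentage and a binomial 95% confidence interval. Neither population is defined in the supplied text.

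The treatment section plans that "Each patient will undergo 2 procedures, to treat all metastases". The second biopsy for the primary endpoint is taken "4-6 weeks after the first RF in a second procedure on another initially untreated metastasis".

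**The concern.** A complication rate describes what happened to the patients who were exposed to the procedure, so its natural denominator is everyone in whom a procedure was started. The plan uses a set chosen by conditions that may be settled after exposure.

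The primary endpoint needs tissue from a second procedure weeks after the first. If that requirement also defines who is evaluable, a patient whose first procedure led to a complication and who had no second procedure would be missing from the complication count. A reader of the final percentage could not see this. With 20 patients, each one is worth 5 percentage points.

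What is at stake is how faithfully procedural risk is reported. The paired-biopsy primary endpoint is not affected.

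**Working it through.** **No plan figure to reproduce.** The sample size of 20 rests on recruitment feasibility. The plan gives no expected complication rate, dropout rate or evaluability rate. All risks and counts below are assumptions, and only the 20 patients and the two procedures per patient come from the documents.

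**Step 1. What one patient does to the rate.** Exact (Clopper-Pearson) 95% intervals, assuming 3 of 20 treated patients have a complication:

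| Set analysed | Rate | 95% CI |
|---|---|---|
| All treated, 3/20 | 15.0% | 3.2 to 37.9 |
| One patient with a complication dropped, 2/19 | 10.5% | 1.3 to 33.1 |
| One event-free patient dropped, 3/19 | 15.8% | 3.4 to 39.6 |
| Two event-free patients dropped, 3/18 | 16.7% | 3.6 to 41.4 |

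The direction depends on who is dropped. The interval for 3/20 is 37.9 − 3.2 = 34.7 points wide.

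**Step 2. A patient-level rule requiring both procedures.** Let p be the complication risk at each procedure (independent), d the fraction of first-procedure complications that prevent the second, and w the fraction of patients who miss the second procedure for unrelated reasons. The measure is the percentage of patients with any complication.

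- All treated: p + (1 − p)(1 − w)p
- Patients with both procedures: [p(1 − d) + (1 − p)p] / (1 − pd). Here w cancels.

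Example, p = 0.10, d = 0.5, w = 0: all treated 0.10 + 0.90 × 0.10 = 19.0%; reported (0.05 + 0.09) / 0.95 = 14.7%. The expected number dropped is 20 × 0.10 × 0.5 = 1 patient.

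| p | d | Reported | All treated at w = 0 / 0.2 / 0.3 | Shift in points |
|---|---|---|---|---|
| 5% | 0.25 | 8.6% | 9.75 / 8.8 / 8.3% | −1.1 / −0.2 / +0.3 |
| 5% | 0.5 | 7.4% | 9.75 / 8.8 / 8.3% | −2.3 / −1.4 / −0.9 |
| 10% | 0.25 | 16.9% | 19.0 / 17.2 / 16.3% | −2.1 / −0.3 / +0.6 |
| 10% | 0.5 | 14.7% | 19.0 / 17.2 / 16.3% | −4.3 / −2.5 / −1.6 |

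Patients who miss the second procedure for unrelated reasons were at risk only once. Removing them raises the per-patient rate, and this can offset or reverse the downward pull.

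**Step 3. The other unit.** The plan does not say whether complications are counted per patient or per procedure. Per procedure, the all-treated rate is p, and the rate in patients with both procedures is the mean of p(1 − d)/(1 − pd) and p. For p = 10% this gives 8.8% (d = 0.25) or 7.6% (d = 0.5). For p = 5% it gives 4.4% or 3.8%. The shifts are 0.6 to 2.4 points downward and do not depend on w.

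**Step 4. Loss through eligibility.** If a treated patient later found ineligible is removed for reasons unrelated to outcome, the assumed 3/20 becomes 15.8% with probability 17/20 and 10.5% with probability 3/20. The expected value is 0.85 × 15.8 + 0.15 × 10.5 = 15.0%, so there is no average bias. If 10% of patients were ineligible and had twice the risk of the others, 15.0% would be reported as 15.0 / (0.9 + 0.1 × 2) = 13.6%.

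**The case against.** The strongest reply is that the text shows undefined wording rather than an exclusion. The endpoints need different data: biopsies, blood samples around each RF, follow-up scans and complication grades. One biopsy-based rule would discard usable blood and scan data, so judging evaluability endpoint by endpoint is a natural reading, and under it the loss through evaluability is nil. This stands as a possibility. It does not settle the matter, because the plan names a single population for all these endpoints and sets it apart from the eligible one.

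On eligibility, the plan lists "Compliance with eligibility criteria" among the characteristics described in the eligible set. That item would have nothing to show if the set held only patients meeting every criterion, so the term may mean little more than included. Contraindications are also screened beforehand: "Decision on local treatment taken during the multidisciplinary meeting or during an Interventional Radiology opinion meeting (no contraindication"). This part of the concern is therefore weak.

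The plan also describes the procedures performed in the wider eligible set, so a missed second RF would be visible there. That helps a careful reader but does not correct the complication percentage. The supplied text is a synopsis, and a fuller text may define the populations.

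A reader might infer that the plan necessarily biases the complication rate downward, or that a real rate could be reported as zero. The documents support neither. The first ignores patients lost for unrelated reasons. The second needs every patient with a complication to be dropped, and nothing in the text suggests that.

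**Conclusion.** The point holds in a limited form. As written, the plan places complications in a restricted population and offers no all-treated alternative. Whether this removes anyone depends on what evaluable means. If it is a patient-level condition tied to the second procedure, the net per-patient shift under the assumed risks, with w up to 0.3, runs from 0.6 points upward to 4.3 points downward. Counted per procedure, it is at most 2.4 points downward. These results rest on independent risks of 5% to 10% per procedure and on assumed values of d and w. They are small beside an interval of about 35 points.

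Severity is minor: the study is exploratory and descriptive, and nothing in the supplied text makes a decision depend on this rate. It is still worth correcting, because a wide interval is visible to the reader and a selective denominator is not.

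**What to change.** In DATA STATISTICAL ANALYSIS, state that complications are analysed in every patient with at least one RF or biopsy procedure started, regardless of eligibility or evaluability. Keep the eligible and evaluable population for the biopsy and biological endpoints. If no fuller text defines the two terms, a short definition of each would help, but the all-treated denominator does not depend on it.

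The cost is wording only, with no extra patients or visits provided that complications are recorded at each procedure. Denominators will then differ between complications and the other endpoints, and the complication rate may look slightly less favourable.

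### Is the binomial 95% interval too narrow for the outcome of treated metastases, given that one patient contributes several sites?

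*Combined protocol and SAP*

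**What the plan says.** All the relevant text is in the synopsis.

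- **Endpoint** (ENDPOINTS, secondary): "Assessment of the progress of treated sites and of any distant metastatic disease by scans at 3, 6, 9 and 12 months". No progression criterion, yes/no outcome or site-level rate is defined.
- **Interval** (DATA STATISTICAL ANALYSIS): "Qualitative variables will be described based on frequency, percentage and 95% confidence interval (binomial law"). Quantitative variables have a separate line, with means or medians according to normality.
- **Who is analysed** (same section): the endpoint analysis "will concern the eligible and evaluable population".
- **Size and purpose** (same section): "20 patients will be included in this study", and "This exploratory study is not based on a statistical hypothesis but on feasibility criteria in terms of recruitment".
- **Sites per patient** (INCLUSION CRITERIA): "Lung metastases bilateral (or unilateral if: number ≥ 5 and requiring two interventions"), with a ceiling in the imaging criterion, "finding lung metastases of which no more than 10 can be" treated over the two sessions. The procedures section adds: "Each patient will undergo 2 procedures, to treat all metastases".

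Nowhere does the supplied text name the patient or the lesion as the unit for the treated-site outcome.

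**The concern.** The endpoint is worded in terms of sites, the only interval offered for a proportion assumes independent units, and the design ensures that patients bring more than one site. Bilateral disease means at least two metastases. Unilateral disease qualifies only with five or more, and up to ten may be treated. Lesions in one patient share a tumour, any chemotherapy and an operating team, so their outcomes are plausibly correlated.

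If an analyst added up all ablated lesions and applied the binomial formula, 20 patients could be presented as 100 or 200 independent observations. The estimated rate would keep its meaning as a per-lesion rate, but its interval would be too short. In a study whose output is descriptive estimates with intervals, that would overstate how well local control is known.

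**Working it through.** The plan has no figure to reproduce here: the 20 patients rest on recruitment feasibility, with no precision target. The check asks how a 95% binomial interval behaves under each possible unit.

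**Inputs from the synopsis:** 20 patients; a 95% binomial interval, taken here as the exact (Clopper-Pearson) form because the form is not specified; 2 to 10 treated sites per patient.

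**Assumed, because the documents do not give them:** site progression rate p of 5%, 10% or 20%; ICC of 0.05 to 0.3; the same number of sites m in every patient.

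**Unit = site, pooled.** Each patient's count of progressing sites is beta-binomial with mean m·p and correlation ICC. The distribution of the total over 20 patients is found by exact convolution, and coverage is the probability that the exact interval on 20·m sites contains p. The variance is inflated by the design effect 1 + (m − 1)·ICC.

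| Sites per patient | ICC | Design effect | Coverage at p = 5% / 10% / 20% |
|---|---|---|---|
| 2 | 0.05 | 1.05 | 98.4 / 96.6 / 96.9% |
| 2 | 0.3 | 1.30 | 97.2 / 94.2 / 94.7% |
| 4 | 0.05 | 1.15 | 95.1 / 96.6 / 95.1% |
| 4 | 0.3 | 1.90 | 87.1 / 89.9 / 87.4% |
| 5 | 0.05 | 1.20 | 97.0 / 93.4 / 94.9% |
| 5 | 0.3 | 2.20 | 89.3 / 82.1 / 85.0% |
| 10 | 0.05 | 1.45 | 92.6 / 92.3 / 91.0% |
| 10 | 0.3 | 3.70 | 73.5 / 72.6 / 70.8% |

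The shortfall ranges from nil to about 24 points (95 − 70.8). It has no fixed starting point. At 5 sites there is none when p = 5% and ICC = 0.05 (97.0%), while at 4 sites with ICC 0.3 coverage is already 87-90%.

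**Example.** Suppose 10 of 100 sites progress (20 patients, 5 sites each).

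- Pooled exact interval: 4.9-17.6%.
- Normal half-width: 1.96 × √(0.1 × 0.9 / 100) = 5.9 points.
- With ICC 0.2 the design effect is 1 + 4 × 0.2 = 1.8, and the half-width becomes 5.9 × √1.8 = 7.9 points.

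**Unit = patient.** Patients are independent, so correlation between lesions in one patient does not disturb the interval, and the exact form covers at least 95%. If 2 of 20 patients have any treated site progressing, the interval is 1.2-31.7%.

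**Which unit does the text support?** The endpoint line names what the scans look at: treated sites and distant disease, at four visits. The analysis section names whom the results describe: the eligible and evaluable members of a sample of 20 patients. Distant metastatic disease, in the same endpoint sentence, is naturally a patient-level status. No line calls for a lesion denominator.

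**The case for a change.** The strongest argument for a change is that the unit is not stated, several sites per patient are built into eligibility, and in a study without hypotheses the intervals are the product. The unit also changes the quantity estimated. With 10% of sites progressing and ICC 0.1-0.3, the share of patients with any treated site progressing is about 16-18% at 2 sites per patient and 36-52% at 10. A silent choice made after seeing the data could therefore matter to a reader, and naming the unit would take a sentence.

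Part of this stands. The supplied text does leave the unit open, and the coverage loss under pooling is real where sites are many and correlation is moderate.

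The rest does not carry the point. A faulty interval needs three steps that the plan does not take: defining a yes/no outcome for each lesion, pooling lesions across patients, and ignoring the pooling when the interval is computed. The outcome could equally be lesion size, which falls under the line for quantitative variables, or a status per patient. Ten sites is a ceiling, not an expected count. The five for unilateral disease counts metastases present, some of which may be left untreated because they are small. The supplied text is also a synopsis, where the unit of a secondary imaging outcome is often left to fuller text.

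**Conclusion.** No change is needed. The unit is a gap that an analyst fills sensibly when reporting: taken per patient, as the analysis population suggests, the stated binomial interval is sound. The possible harm is conditional on pooling sites as a yes/no outcome. Coverage would then be about 94-98% at 2 sites per patient, 82-97% at 5 and 71-93% at 10. These figures rest on an assumed progression rate of 5-20%, an assumed ICC of 0.05-0.3, equal site counts and the exact interval. Even then, only the reported precision of one descriptive secondary outcome in an exploratory study would suffer. The primary endpoint, the sample size and any decision are untouched. Anyone who does report a per-lesion rate should name the denominator and allow for clustering by patient, which is ordinary practice at the reporting stage and needs no amendment.
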